Acquired epileptic aphasia, Acute encephalitis with refractory, repetitive partial seizures, Alcoholic seizure, Atonic seizures, Atypical benign partial epilepsy, Automatism epileptic, Autonomic seizure, Baltic myoclonic epilepsy, Benign familial neonatal convulsions, Benign rolandic epilepsy, Biotinidase deficiency, Change in seizure presentation, Clonic convulsion, Complex partial seizures, Convulsion in childhood, Convulsion neonatal, Convulsions local, Convulsive threshold lowered, Deja vu, Double cortex syndrome, Dreamy state, Drug withdrawal convulsions, Early infantile epileptic encephalopathy with burst-suppression, Eclampsia, Epilepsy, Epileptic aura, Epileptic psychosis, Febrile convulsion, Frontal lobe epilepsy, Generalised non-convulsive epilepsy, Generalised tonic-clonic seizure, Glucose transporter type 1 deficiency syndrome, Hemimegalencephaly, Hyperglycaemic seizure, Hypocalcaemic seizure, Hypoglycaemic seizure, Hyponatraemic seizure, Idiopathic generalised epilepsy, Infantile spasms, Juvenile myoclonic epilepsy, Lafora's myoclonic epilepsy, Lennox-Gastaut syndrome, Migraine-triggered seizure, Molybdenum cofactor deficiency, Myoclonic epilepsy, Myoclonic epilepsy and ragged-red fibres, Partial seizures, Partial seizures with secondary generalisation, Petit mal epilepsy, Polymicrogyria, Post stroke epilepsy, Post stroke seizure, Postictal headache, Postictal paralysis, Postictal psychosis, Postictal state, Post-traumatic epilepsy, Psychomotor seizures, Focal dyscognitive seizures, Schizencephaly, Seizure, Seizure anoxic, Seizure cluster, Seizure like phenomena, Severe myoclonic epilepsy of infancy, Simple partial seizures, Status epilepticus, Sudden unexplained death in epilepsy, Temporal lobe epilepsy, Tonic clonic movements, Tonic convulsion, Tonic posturing, Topectomy, Uncinate fits

AEDECOD (MedDRA v19.1)

chamber fibrin, Anterior chamber flare, Anterior chamber inflammation, Agueous fibrin, Autoimmune retinopathy, Autoimmune uveitis, Behcet's syndrome, Birdshot chorioretinopathy, Blau syndrome, Blindness, Blindness transient, Blindness unilateral, Chemical iritis, Chorioretinitis, Chorioretinopathy, Choroiditis, Ciliary hyperaemia, Cystoid macular oedema, Cytomegalovirus chorioretinitis, Eales' disease, Endophthalmitis, Exudative retinopathy, Eye inflammation, Fuchs' syndrome, Glaucomatocyclitic crises, Iridocyclitis, Iritis, Macular oedema, Non-infectious endophthalmitis, Noninfective chorioretinitis, Noninfective retinitis, Ocular toxicity, Ocular vasculitis, Optic discs blurred, Panophthalmitis, Photophobia, Photopsia, Retinal exudates, Retinal oedema, Retinal pigment epitheliopathy, Retinal toxicity, Retinal perivascular sheathing, Retinal vasculitis, Retinitis, Subretinal fluid, Sudden visual loss, Susac's syndrome, Sympathetic ophthalmia, Traumatic iritis, Tubulointerstitial nephritis and uveitis syndrome, Uveitis, Uveitis-glaucoma-hyphaema syndrome, Vision blurred, Visual acuity reduced, Visual field defect, Visual impairment, Vitreal cells, Vitreous floaters, Vitreous opacities, Vitritis, Vogt-Koyanagi-Harada syndrome

Acute zonal occult outer retinopathy, Anterior chamber cell, Anterior

Renal AEOI (for PRT) / laboratory related events

Ocular AEOI (for Posterior Uveitis)

Aminoaciduria, Beta-N-acetyl D glucosaminidase increased,
Hyperphosphaturia, Renal glycosuria, Acquired aminoaciduria,
Hyperchloraemia, Protein urine, Protein urine present, Proteinuria, Urine
phosphorus abnormal, Beta-N-acetyl D glucosaminidase abnormal, Blood
chloride increased, Blood phosphorus decreased, Blood potassium
decreased, Blood uric acid abnormal, Blood uric acid decreased, Glucose
urine present, Glycosuria, Hyperuricosuria, Hypokalaemia,
Hypophosphataemia, Amino acid level abnormal, Amino acid level increased,
Urine phosphorus increased, Urine uric acid abnormal, Urine uric acid
increased

Renal AEOI (for PRT) / clinical events

Polydipsia, Polyuria, Nephropathy toxic, Renal tubular disorder, Chronic kidney disease, Fanconi syndrome, Fanconi syndrome acquired, Renal tubular acidosis

AEDECOD (MedDRA v19.1)

Bone AEOI (for fractures) / Osteomalacia	Hypophosphataemic rickets, Osteomalacia, Chronic kidney disease-mineral and bone disorder, Renal rickets, Rickets
Bone AEOI (for fractures) / Bone Loss/atrophy	Bone atrophy, Bone decalcification, Bone density decreased, Bone formation decreased, Bone loss, Craniotabes, High turnover osteopathy, Hungry bone syndrome, Osteodystrophy, Osteolysis, Osteoporosis circumscripta cranii, Osteopenia, Senile osteoporosis, Osteoporosis, Cementoplasty
Bone AEOI (for fractures) / Fracture, possibly osteoporotic	Femoral neck fracture, Hip fracture, Lumbar vertebral fracture, Osteoporotic fracture, Spinal compression fracture, Spinal fracture, Thoracic vertebral fracture

Bone AEOI (for fractures) / Fracture other

Acetabulum fracture, Ankle fracture, Atypical femur fracture, Atypical fracture, Avulsion fracture, Cervical vertebral fracture, Chance fracture, Clavicle fracture, Closed fracture manipulation, Comminuted fracture, Complicated fracture, Compression fracture, Elevation skull fracture, Epiphyseal fracture, External fixation of fracture, Femur fracture, Fibula fracture, Foot fracture, Forearm fracture, Fracture, Fracture delayed union, Fracture displacement, Fracture malunion, Fracture nonunion, Fracture pain, Fracture reduction, Fracture treatment, Fractured ischium, Fractured sacrum, Fractured coccyx, Greenstick fracture, Hand fracture, Humerus fracture, Ilium fracture, Internal fixation of fracture, Limb fracture, Lower limb fracture, Multiple fractures, Open reduction of fracture, Open reduction of spinal fracture, Osteochondral fracture, Osteosynthesis, Patella fracture, Pathological fracture, Pelvic fracture, Periprosthetic fracture, Pubis fracture, Radius fracture, Rib fracture, Sacroiliac fracture, Scapula fracture, Skull fracture, Skull fractured base, Spinal fusion fracture, Sternal fracture, Stress fracture, Tibia fracture, Torus fracture, Traumatic fracture, Ulna fracture, Upper limb fracture, Wrist fracture

AEDECOD (MedDRA v19.1)

Bone AEOI (for fractures) / Other Bone Events

Bone density abnormal, Bone disorder, Bone erosion, Bone lesion, Bone formation test abnormal, Bone fragmentation, Bone metabolism disorder, Bone pain, Bone resorption test abnormal, Bone scan abnormal, Bone development abnormal, Bone swelling, Epiphysiolysis, Nuclear magnetic resonance imaging spinal abnormal, Osteonecrosis, Osteonecrosis of jaw, Secondary sequestrum, Skeletal injury, Skeletal survey abnormal, Skull X-ray abnormal, Spinal X-ray abnormal, Vertebral lesion, Vertebral wedging, X-ray limb abnormal, X-ray of pelvis and hip abnormal, Bone densitometry

ATTACHMENT 3

AE preferred terms (as available in AE Clinical database) are assigned an Adverse Drug Reaction System Organ Class (ADRSOC) and Adverse Drug Reaction (ADRCAT) according to the table below.

Adverse Drug Reaction System Organ Class	Adverse Drug Reaction	Adverse Event Preferred Term
GASTROINTESTINAL DISORDERS	ABDOMINAL DISTENSION	ABDOMINAL DISTENSION
	ABDOMINAL PAIN	ABDOMINAL PAIN
		ABDOMINAL PAIN LOWER
		ABDOMINAL PAIN UPPER
	DIARRHOEA	DIARRHOEA
		FREQUENT BOWEL MOVEMENTS
	DYSPEPSIA	DYSPEPSIA
	FLATULENCE	FLATULENCE
	NAUSEA	NAUSEA
	PANCREATITIS ACUTE	PANCREATITIS
		PANCREATITIS ACUTE
	VOMITING	VOMITING
GENERAL DISORDERS AND ADMINISTRATION SITE CONDITIONS	ASTHENIA	ASTHENIA
	FATIGUE	FATIGUE
HEPATOBILIARY DISORDERS	ACUTE HEPATITIS	HEPATITIS
		HEPATITIS ACUTE
		HEPATOTOXICITY
IMMUNE SYSTEM DISORDERS	(DRUG) HYPERSENSITIVITY	DRUG HYPERSENSITIVITY
		HYPERSENSITIVITY

Approved, Date: 25 April 2018

Adverse Drug Reaction System Organ Class	Adverse Drug Reaction	Adverse Event Preferred Term
	IMMUNE RECONSTITUTION SYNDROME	IMMUNE RECONSTITUTION INFLAMMATORY SYNDROME
		IMMUNE RECONSTITUTION SYNDROME
METABOLISM AND NUTRITION DISORDERS	ANOREXIA	DECREASED APPETITE
	DIABETES MELLITUS	DIABETES MELLITUS
		DIABETES MELLITUS INADEQUATE CONTROL
		TYPE 2 DIABETES MELLITUS
		GLUCOSE TOLERANCE IMPAIRED
	LIPODYSTROPHY	FACIAL WASTING
		FAT REDISTRIBUTION
		FAT TISSUE INCREASED
		LIPOATROPHY
		LIPODYSTROPHY ACQUIRED
		LIPOHYPERTROPHY
		PARTIAL LIPODYSTROPHY
MUSCULOSKELETAL AND CONNECTIVE TISSUE DISORDERS	MYALGIA	MYALGIA
	OSTEONECROSIS	OSTEONECROSIS
NERVOUS SYSTEM DISORDERS	HEADACHE	HEADACHE
PSYCHIATRIC DISORDERS	ABNORMAL DREAMS	ABNORMAL DREAMS
REPRODUCTIVE SYSTEM AND BREAST DISORDERS	GYNAECOMASTIA	GYNAECOMASTIA
		HYPERTROPHY BREAST
SKIN AND SUBCUTANEOUS TISSUE DISORDERS	ANGIOEDEMA	ALLERGIC OEDEMA
		ANGIOEDEMA

46

Adverse Drug Reaction System Organ Class	Adverse Drug Reaction	Adverse Event Preferred Term
		CIRCUMORAL OEDEMA
		CONJUNCTIVAL OEDEMA
		CORNEAL OEDEMA
		EPIGLOTTIC OEDEMA
		EYE OEDEMA
		EYE SWELLING
		EYELID OEDEMA
		FACE OEDEMA
		GINGIVAL OEDEMA
		GINGIVAL SWELLING
		GLEICH'S SYNDROME
		HEREDITARY ANGIOEDEMA
		LARYNGEAL OEDEMA
		LARYNGOTRACHEAL OEDEMA
		LIP OEDEMA
		LIP SWELLING
		OCULORESPIRATORY SYNDROME
		OEDEMA MOUTH
		OROPHARYNGEAL SWELLING
		PALATAL OEDEMA
		PERIORBITAL OEDEMA
		PHARYNGEAL OEDEMA
		SCLERAL OEDEMA
		SMALL BOWEL ANGIOEDEMA
		SWELLING FACE
		SWOLLEN TONGUE

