2.2. Visit Windows

2.2.1. Trial Phases

Phases will be constructed for each subject as follows for adverse events, concomitant therapies, and for the determination of the worst-case/toxicity/change in the cross-tabulations.

Trial phase	Start date	End date
Screening	Minimum of Date of signing the informed consent and Date of the screening visit	1 day before start of treatment
Comparative	Date of the first intake (after	For ongoing subjects, in order of priority:
Treatment Phase	randomization)	- Week 48 visit date;
		if missing then;
		 Projected Week 48 visit date, where projected Week 48 visit date = baseline visit date + (7 *48)
		In case of withdrawal use:
		 Minimum(last intake date of study drug, study withdrawal date) +2 days
	Comparative treatment phase	If a subject switches prior to Week 96:
	end date +1 day	 Minimum(Date of last double-blind intake +2 days, Start Date of first Open Label D/C/F/TAF intake)
		If a subject never switches prior to Week 96:
		- Week 96 visit date;
		if missing then;
		 Projected Week 96 visit date, where projected Week 96 visit date = baseline visit date + (7 *96)
		In case of withdrawal prior to switching use:
		Minimum (last intake date of study drug, study withdrawal date) + 2 days
Single Arm	Extended double-blind	- Week 96 visit date;
treatment phase (Switch	treatment phase end date +1 day	if missing then;
to Week 96) *		 Projected Week 96 visit date, where projected Week 96 visit date = baseline visit date + (7 *96)
		In case of withdrawal after switch use:
		 Minimum (last intake date of study drug, study withdrawal date) + 2 days
Follow-up	Maximum (end date of extended double-blind treatment phase, end date of single arm treatment phase) +1 day	Trial termination date for all groups (date of last contact)

^{*} The 3-7 WEEKS AFTER UNBLINDING visit will be handled as follows:

Data up to each subject's Week 96 visit are in scope for this analysis; in addition DXA data (DP domain) up to Week 96 visit+28 days, and if applicable, any (confirmatory) viral load or genotype/phenotype results immediately subsequent to Week 96 (up to 6 weeks) will also be included in this analysis.

⁻ All efficacy assessments collected at this visit will be attributed to the DRV/COBI FDC + FTC/TDF FDC regimen

⁻ All safety assessments collected at this visit will be attributed to the D/C/F/TAF FDC regimen

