3.5. Protocol Deviations

All major protocol deviations will be tabulated and listed by treatment arm and overall. The proportion of subjects with one or more major protocol deviation that led to exclusion from the per protocol analysis set (see Attachment 1) will also be tabulated.

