4.1.3. FDA Snapshot Approach and Time to Loss of Virologic Response Algorithm (TLOVR)

FDA Snapshot approach (applying 20/50/200 copies/mL as threshold): The Snapshot approach will classify subjects into 3 outcome categories: "virologic success", "virologic failure", or "no viral load data in the Week 96 visit window". Several subcategories of the outcome will also be presented in the analysis and are shown below. The categories below are mutually exclusive such that a subject will be included in one (sub)category. If a subject discontinues in the time window but also has an HIV-RNA value in the time window then the viral load value will be used to classify the subject's category.

- Virologic success:
 - Last available HIV RNA <20/50/200 copies/mL in the Week 96 visit window (Week 90-102)
- Virologic failure:
 - Last available HIV RNA ≥20/50/200 copies/mL in the Week 96 visit window (Week 90-102)
 - Virologic failure leading to discontinuation
 - o Discontinued due to other reason (i.e., other than AE/death or virologic failure) and last available HIV RNA ≥20/50/200 copies/mL
- No viral load data in the Week 96 visit window:
 - Discontinued due to AE/death (subjects will be classified in this category if discontinued prior to Week 96 window regardless of HIV RNA level)
 - O Discontinued due to other reason (i.e., other than AE/death or virologic failure) and the last available HIV RNA <20/50/200 copies/mL (or missing)
 - o Missing data during the Week 96 visit window but on study

'Virologic failure' as reason for discontinuing the trial was inadvertently not included in the Study Termination eCRF page. Therefore, whether a subject would be classified into the subcategory 'Virologic failure leading to discontinuation' will be determined by a medical assessment of the comment fields and other specification reasons for discontinuation to determine if anyone discontinued the trial due to lack of efficacy reasons. A current list of comments and other specification reasons are documented in Attachment 5, and will be used to programmatically identify such subjects. Upon further clinical evaluation additional comments or other specification reasons might need to be added, and these will be documented in the DPS. An identified subject will be classified to the Snapshot categories as follows:

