- Data within window: If an identified subject has HIV RNA value within the window, the last HIV RNA value will be used to classify the subject as either at or above the threshold or below the threshold
- No data within window: If an identified subject does not have an HIV RNA value in window, then regardless of the last HIV RNA value the subject will be classified as "Virologic failure leading to discontinuation"

Virologic response will then be categorized as follows: Yes (virologic success), or No (virologic failure and no viral load data in the Week 96 visit window).

The Snapshot approach will also be displayed over time by analysis time point, and will follow the same logic as defined above (please see Section 2.2.2 for visit intervals)

Imputations for missing values

The following imputation method is used to calculate **virologic response** at a given time point:

- observed case: subjects with a missing value are disregarded in the analysis for that time point.
- TLOVR: responders/non-responders are defined according to the FDA Time To Loss Of Virologic Response algorithm; a subject is considered a responder at a given time point if the applicable HIV-RNA criterion is fulfilled at that time point and at the subsequent time point; a subject is considered a confirmed non-responder at a time point in the following situations in order of precedence:
 - o the subject shows a 'rebound' HIV-RNA value (>=threshold copies/mL) at that time point and the subsequent time point;
 - o the subject shows a confirmed rebound at an earlier time point (irrespective of resuppression of viral load)
 - o the subject (permanently) discontinued at that time point or before
 - intermittently missing values are considered as response if the immediately preceding and following visits demonstrated response; in case the subject had not reached the next visit yet, no imputation is performed for the missing time points, unless the subject had discontinued the trial.
 - Remark: in case multiple virologic response observations are available within the same time window, all observations are used to determine TLOVR-imputed response for that time window. In case the subject has not reached the next visit yet, this subject is left out of the analysis for the missing time points.

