- Subjects with no post-baseline viral load measurement (e.g., discontinued within 2 weeks).

29

Sequence No.	Description	Protocol Deviation coded term (DVDECOD)	Exclude from PP	
1	Screening plasma HIV-1 RNA level < 1,000 copies/mL	Entered but did not satisfy criteria	Yes	
2	The subject uses disallowed concomitant therapy specified in the protocol.	Entered but did not satisfy criteria	Yes	
3	The subject has any known allergies to the excipients of the D/C/F/TAF, or DRV/COBI, or TDF/FTC tablets, but the subject was randomized	Entered but did not satisfy criteria	Yes	
4	The dose of Investigational treatment arm (D/C/F/TAF tablet) or the active control arm was temporarily not according to protocol for more than 4 consecutive weeks.	Received wrong treatment or incorrect dose (missed dose or extra dose)	Based on >4 weeks period.	
5	The intake of Investigational treatment arm (D/C/F/TAF tablet) or the active control arm was interrupted for toxicity reasons for more than 4 consecutive weeks.	Received wrong treatment or incorrect dose (missed dose or extra dose)	In that case classified as major and excluded from PP	
6	The intake of Investigational treatment arm (D/C/F/TAF tablet) or the active control arm was interrupted for non - toxicity reasons for more than 4 consecutive weeks, or cumulatively for more than 8 weeks.	Received wrong treatment or incorrect dose (missed dose or extra dose		
7	The subject takes disallowed medication as defined per protocol.	Received a disallowed concomitant treatment	Yes (adjudication based on drug/class and duration).	
8	Subjects not showing genotypic susceptibility to DRV, FTC, TFV	Entered but did not satisfy criteria	Yes	
9	The subject missed two or more consecutive planned visits in the trial	Other	Yes	

Approved, Date: 25 April 2018

Sequence No.	Description	Protocol Deviation coded term (DVDECOD)	Exclude from PP
10	Misallocation of Medkits was observed during Dosage and administration of study drug and subject treated differently than what they were randomized to for more than 4 weeks	Other	Yes
11	After achieving confirmed (consecutive) HIV-1 RNA <50 copies/mL prior to Week 96 and scheduled Week 96 achieving HIV-1 RNA ≥ 50 copies/mL or >1log ₁₀ increase in HIV-1 RNA from the nadir at scheduled Week 96, but no retest in Week 96 window (90-102 weeks)	Other	Yes
12	Subject missed the Week 96 visit.	Other	Yes

31

ATTACHMENT 2

Adverse Events of Interest: List of Preferred Terms

AEOI	AEDECOD (MedDRA v19.1)

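### SAP Attachment 1 item 11 removes only Snapshot failures from the per-protocol set, so taken alone it raises the Week 96 <50 copies/mL rate

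*SAP*

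**What the plan says.** Attachment 1 of the SAP lists the predefined major protocol deviations and marks those that remove a subject from the PP set. Item 11 is marked Yes. Its first limb reads "After achieving confirmed (consecutive) HIV-1 RNA <50 copies/mL prior to Week 96 and scheduled Week 96 achieving HIV-1 RNA ≥ 50 copies/mL". Its second limb is a >1 log10 "increase in HIV-1 RNA from the nadir at scheduled Week 96". Both are followed by "but no retest in Week 96 window (90-102 weeks").

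SAP 4.1.3 defines virologic failure in the Week 96 Snapshot by "Last available HIV RNA ≥20/50/200 copies/mL in the Week 96 visit window (Week 90-102"), and codes response as "No (virologic failure and no viral load data in the Week 96 visit window"). It does not require a confirmatory sample.

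SAP 2.3.1.2 commits to a PP analysis as a check on robustness, on the ground that intent-to-treat may not be conservative for noninferiority. Protocol 11.2 gives three examples of PP exclusions: baseline resistance, interfering co-medication and poor adherence.

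A retest was possible. The protocol's Time and Event Schedule and section 9.1.1 both allow unscheduled samples to confirm virologic failure. SAP 2.2.1 adds that "any (confirmatory) viral load or genotype/phenotype results immediately subsequent to Week 96 (up to 6 weeks) will also be included in this analysis".

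**The concern.** The exclusion is triggered by the endpoint value together with a missing retest. Take two subjects who both attend Week 96 and are both not retested. The one at 40 copies/mL stays in the PP set and the one at 60 copies/mL leaves it. A subject who is retested stays in whatever the second result shows. The only group that disappears is unretested failures.

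The protocol's own examples of PP exclusions are things that might cause altered efficacy. Item 11 selects partly on the Week 96 result. At stake is whether the PP Snapshot rate can serve as a robustness check when one of its exclusion rules moves that rate in the favourable direction.

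**Working it through.** **Inputs.** The item 11 conditions come from SAP Attachment 1 and the Snapshot rules from SAP 4.1.3. The planned 335 per arm and the 80% response rate come from Protocol 11.3 and SAP 1.4, where 80% is the Week 48 planning rate. The number meeting item 11 is not in the documents. I assume 1 to 5 per arm for illustration, and I use about 90% as a second illustrative rate.

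**The plan's own figure.** The plan gives no PP rate and no count for item 11. The planning inputs themselves reproduce. With 335 per arm and 80% in both arms, SE = √(2 × 0.8 × 0.2 / 335) = 0.0309, and power = Φ(0.10/0.0309 − 1.96) = 89.9%, against 90% stated.

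**Step 1: class of the excluded subjects, ≥50 limb.** With no retest, the scheduled Week 96 value is the last value in Weeks 90-102. At ≥50 copies/mL it is a virologic failure and is coded as non-response. Protocol 9.1.1 allows ±7 days, so a visit on schedule falls in Weeks 95-97, inside the window. A sample outside Weeks 90-102 is the exception.

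**Step 2: the log10 limb.** This can be read in two ways.
- If earlier confirmed suppression applies to it too, it adds nobody beyond Step 1.
- If it stands alone, as in the rebound definitions of Protocol 9.2.2.1 and SAP 4.3.2.3, it can add subjects who were never suppressed. SAP 4.1.2 scores results below 20 as 19, so the nadir is at least 19 and a rise of more than 1 log10 means more than 19 × 10 = 190 copies/mL. These subjects are also non-responders at <50.

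**Step 3: effect on the rate.** Let s be the number of responders, N = 335, and n the number removed. The rate changes from s/N to s/(N − n), which is larger whenever n ≥ 1 and s ≥ 1.

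| s | Rate with all kept | n = 1 removed | n = 5 removed |
|---|---|---|---|
| 268 | 80.00% | 268/334 = 80.24% (+0.24) | 268/330 = 81.21% (+1.21) |
| 302 | 90.15% | 302/334 = 90.42% (+0.27) | 302/330 = 91.52% (+1.37) |

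**Step 4: what would cancel it.** Suppose other PP rules remove m responders. The net change is zero when (s − m)/(330 − m) = s/335, so m = 5s/(335 − s). This gives 5 × 268/67 = 20 responders at 80%, and 5 × 302/33 = 45.8, about 46, at 90%.

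**Step 5: other thresholds and algorithms.** At <200 copies/mL a subject at 50-199 is a success, so the effect can reverse. If all 5 removed were in that range, 285/335 = 85.07% becomes 280/330 = 84.85% (−0.23 from unrounded values), and 318/335 = 94.93% becomes 313/330 = 94.85% (−0.08). For TLOVR I claim no direction: it needs a value at the following time point, and "In case the subject has not reached the next visit yet, this subject is left out of the analysis for the missing time points".

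**The case against.** The best defence is that an unretested rebound is unresolved. Snapshot takes the last in-window value, so a retest below 50 would have turned the subject into a success. Keeping these subjects as failures therefore understates the rate that full retesting would give, if any would have resuppressed. That is true, but exclusion is not neutral either. If a fraction r would have resuppressed, full retesting gives (s + rn)/N. Exclusion gives s/(N − n), which is too high unless r is at least s/(N − n). In the examples above that is between 80.2% and 91.5%. Confirmation also belongs to the protocol's rebound definition and is not part of Snapshot.

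A second argument is that other rules, such as item 12 (missed Week 96 visit), will also mostly remove Snapshot non-responders. That stands as a fact, but item 12 turns on a missed visit and not on the observed viral load.

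Third, a missed retest might be a genuine procedural violation. That rests on the Protocol Deviation Criteria document, which is not available here. Even so, a violation can be reported without removing the subject from the PP set.

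Three limits stand in full. SAP 4.3.2.1 names no PP output. The number affected is unknown and could be zero. No bias in the difference between arms has been shown.

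**Conclusion.** The concern holds, as a minor point. On the SAP's own rules, item 11 removes only subjects who are Snapshot non-responders at <50 copies/mL, provided the Week 96 sample lies in Weeks 90-102. Its separate effect on the PP rate is therefore upward whenever anyone meets it. The direction is firm. The size depends on an unknown count and is about a quarter of a point per subject removed at 335 per arm. The net difference between PP and intent-to-treat also depends on the other exclusions, and no net direction is claimed.

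The consequence is small. Intent-to-treat is the primary efficacy set (SAP 2.3.1.1), the Week 96 efficacy analyses are descriptive (SAP 4.1.1), and the Week 48 result lies outside this SAP. Nor would these subjects be hidden, since SAP 3.5 states that "All major protocol deviations will be tabulated and listed by treatment arm and overall".

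**What to change.** In Attachment 1, delete item 11 as a PP exclusion and keep these subjects in the PP set with their Snapshot outcome. They can remain major deviations in the SAP 3.5 tables and listings. The cost is one table edit and, if anyone meets the criterion, a slightly less favourable PP Snapshot rate at <50.

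Two optional additions would help the reader. One is to break down the planned SAP 3.5 tabulation by item number and arm. The other is a supportive PP run that keeps item 12 subjects with their Snapshot outcome. Together they cost one extra breakdown and one supportive table.
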